Development and Evaluation of Video-Based Directly Observed Therapy for Office-Based Treatment of Opioid Use Disorders with Buprenorphine

NCT03779997

APRIL 4, 2021

TAAB SAP Table of Contents

- 1 Study Overview and Design 2
 - 1.1 Target Population..... 2
 - 1.1.1 Study Sites..... 2
 - 1.1.2 Inclusion/Exclusion Criteria 2
 - 1.2 Group Allocation – Randomized..... 3
 - 1.3 Study Outcomes..... 3
- 2 Sample Size Determination 3
- 3 Analysis Plan..... 4
 - 3.1 Analysis Parameters 4
 - 3.2 Primary Analysis (Percentage Opioid Negative Urine Tests) 4
 - 3.3 Secondary Analysis (Retention - Week 12)..... 5
 - 3.4 Exploratory Hypotheses..... 5
 - 3.5 Sensitivity Analyses..... 7
 - 3.6 Additional Model Selection Analyses..... 8
 - 3.7 Sub-group Analyses 8
 - 3.8 Missing Data..... 8
- 4 Data Monitoring 9
 - 4.1 Interim and Safety Analyses 9

Trial of Adherence Application for Buprenorphine Treatment (TAAB) Study Protocol and Statistical Analysis Plan

1 Study Overview and Design

The objective of this study is to compare an innovative mobile health (mHealth) platform to support patients treated for opioid use disorder (OUD) with buprenorphine to treatment-as-usual (TAU). The application will provide video-based directly observed therapy (video-DOT) which may result in better health outcomes for patients and less public health risk for diversion.

All participants will follow the same visit schedule. Interviews will occur at baseline (Week 0) and the final visit (Week 12) and assessments will include questions on current and prior substance use, treatment history, medication adherence, drug diversion, general physical and mental health and treatment satisfaction. A point of care urine drug test (UDT) will also be administered at baseline and all weekly visits which will assess for opioids and other substances. Research staff will review the electronic medical record at baseline and week 12 to assess engagement in treatment. Additionally, at 24 weeks post-enrollment the research staff will complete a review of the electronic medical record and record engagement in clinic treatment, changes in buprenorphine treatment during the study period and the results of clinical urine drug testing if available.

Study type: Pilot Randomized Controlled Trial of a Behavioral Intervention – Video-DOT smartphone application where participants will be asked to record one daily video of themselves confirming daily ingestion of their prescribed buprenorphine.

Primary Purpose: Treatment

Interventional Study Model: Parallel Assignment

Number of Arms: 2

1.1 Target Population

1.1.1 Study Sites

Subjects will be recruited at office-based buprenorphine programs at Harborview Medical Center (University of Washington) and Boston Medical Center (Boston University).

1.1.2 Inclusion/Exclusion Criteria

Inclusion criteria

- 1) ≥18 years old
- 2) Receiving oral (i.e. not injectable) buprenorphine treatment at an office-based buprenorphine program at Harborview Medical Center or at Boston University Medical Center for ≤4 weeks.
- 3) Willing to be randomized to either video-DOT or TAU arms.

Exclusion criteria

- 1) Unable or unwilling to use smart phone (phones to be provided as needed)

- 2) Cognitive impairment (acute or chronic) resulting in inability to provide informed consent
- 3) Researcher's discretion that participant will not be appropriate for participation in the study (e.g. participant is planning on moving away, is knowledgeable of future incarceration during study, or has behavioral issues that may pose safety concerns for clinic and research staff)
- 4) Inability to read and understand English as needed for following in app instructions

1.2 Group Allocation – Randomized

This study is a randomized controlled trial with two arms - TAU and intervention with the application (video-DOT). Group assignment will be randomized through computer randomization procedures using REDCap and randomization lists generated with the random number generator in R. Randomization will be stratified by site (HMC v. BMC). Each site was allotted 99 treatment assignments with half for TAU and half video-DOT in case of potential recruitment and enrollment imbalances between sites (it is anticipated that there will be approximately 40 enrolled participants at each site). The target total sample size is 80. The PIs will be blinded to randomization; other research staff (e.g., research coordinator and assistant) will not be blinded.

1.3 Study Outcomes

Primary Outcome – Percentage of 12 research study UDTs that are negative for opioids between 1 week and 12 weeks post-randomization

Secondary Outcome – Engagement in treatment at week 12

Exploratory Outcomes

1. Engagement in treatment at week 24
2. Number of consecutive weeks with study UDTs negative for opioids during the 12-week study period
3. Self-report of use of illicit opioids in the past 30 days assessed at week 12
4. Percentage of days adherent to buprenorphine by self-report during the 12-week study period
5. Time to occurrence of non-retention
6. Having one or more study UDTs negative for buprenorphine any time during the 12-week study period
7. Having a study UDT positive for stimulants (cocaine, amphetamines or methamphetamines) at week 12
8. Patient satisfaction with treatment at week 12

2 Sample Size Determination

We anticipate that 70% of patients will complete the 12-week intervention period of our pilot trial, and that the percentage of opioid negative urine samples will be approximately 50% in the TAU arm.

The sample size of 80 patients is estimated to provide 69% power to detect the anticipated difference of 20% in the rate of opioid negative samples. The minimal clinically meaningful difference is considered to be 15%, which would require approximately 200 patients to reliably detect.

The final sample size for the Phase III trial will be determined based on the results of the pilot trial.

3 Analysis Plan

3.1 Analysis Parameters

Results of the Generalized Estimating Equations (GEE), Poisson regression, and unequal variance t-test analyses will be reported with 95% confidence intervals and test of the null hypothesis at a significance level of 0.05.

GEE was selected because it accounts for correlation between observations on the same patient over time without requiring assumptions about correlation structure by using “robust” variance estimates.

3.2 Primary Analysis (Percentage Opioid Negative Urine Tests)

The primary analysis is performed to test the following hypothesis:

Primary Hypothesis: Patients in video-DOT arm will have higher percentage of weekly UDTs negative for opioids compared to TAU during the 12 -week intervention period.

Analyses will be done according to the intent-to-treat principle which includes all randomized patients regardless of their compliance with the study protocol. To evaluate the primary hypothesis, we will compare percentage of negative UDTs between the two groups using Generalized Estimating Equations (GEE). Missing urine samples will be assumed to be positive*.

* **NOTE:** As of 3/13/2020 phone visits have occurred at both sites due to the COVID-19 outbreak. For follow-up and final assessment visits by phone, a study UDT sample was not collected. If a clinical UDT result is also not available for a particular phone visit, then the participant’s UDT data for that visit is excluded from the primary analysis.

Primary Outcome Variables

12 Research-UDTs for 5 Opioid Assays (F/U Visits 1-11, and Final):

- Negative for opioids* = negative for the following: Morphine (i.e., “udt_he”), Methadone, Oxycodone, Fentanyl
* Propoxyphene assay was in the original UDTs (Alere iCup); New UDT (Identify Diagnostics) does not include it. Will not include this data in the analysis. Dates new UDT’s first started being used: BMC – 11/6/2019, UW – 11/8/2019.

- (1) On 2/11/2020 a decision was made to code a study UDT as negative if at least one substance was missing but the rest were negative.
 - (a) **Note:** First check the clinical UDT to supplant a missing value. I.e., If the clinical UDT is also missing for that same substance, code the test as negative. If the clinical UDT

is positive for the particular substance that is missing from the study UDT, then code that test as positive.

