3.5 Sensitivity Analyses

The primary analysis will be repeated for each of the following modifications:

1. **Adjusted Analyses:** We will use Generalized Estimating Equations to compare percentage of negative UDTs with adjustment for the following covariates: (see table below)
2. **Missing Data Analyses:** The primary analysis will be repeated using multiple imputations for missing urine samples (rather than assuming all missing are opioid positive). All covariates listed below will be used in the imputation model provided they have less than 20% missing. (See additional details on missing data in [Section 3.8.](#))

3. **Per-protocol Analyses:** The primary analysis will be repeated excluding patients who drop out of the study or are not compliant with study protocol (e.g., submitted 7 or less videos during the first 4 weeks of study involvement). In addition, analyses will use the number of uploaded videos as a measure of compliance to determine whether there is a dose-response effect.

4.

Covariate Table	
1. Site	Seattle or Boston
2. Age	Years
3. Sex	Male, Female
4. Race	Caucasian vs. Non-Caucasian
5. Hispanic Ethnicity	Yes or No
6. Education	Less than High School, High School, Some College, Bachelor's degree or higher
7. Prior Buprenorphine Treatment	Yes or No
8. Homelessness	Yes or No

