3.7 Sub-group Analyses

The primary analysis will be repeated with interaction terms between treatment arm and each of the following sub-group variables:

- a. Site (Boston and Seattle)
- b. Gender (Men vs. Women)
- c. Age (based on median split)
- d. Baseline homelessness

Results will be reported as treatment effect estimates for each sub-group with 95% confidence intervals and tests of the null hypothesis with overall level of significance 0.05 and Bonferroni adjustment for multiple comparisons. In addition, a significance test of the interaction between treatment and each sub-group variable will be conducted at significance level 0.05.

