3.8 Missing Data

All efforts will be made to complete study visits/procedures and avoid missing data. However, we anticipate there will be missing data, in particular for the primary outcome. As has been the convention in other studies, we will assume that missing UDT results are positive (unless a visit was conducted by phone due to COVID-19). However, we will also conduct analyses to better understand the nature of missing data and carry out multiple imputation analysis in order to determine the impact of missing UDTs.

We will assess missing data by comparing baseline characteristics between participants lost to follow-up (who are missing data on the primary or secondary outcome) versus those who are not.

Missing data patterns will also be evaluated including the frequency and percentage of those missing for each variable and the distribution of the number of variables missing. Patterns of missing urine samples will be described and compared between treatment arms.

Data collected to the point of lost to follow-up will be compared to the data of those who complete the study to examine possible missing data mechanisms, e.g., missing completely at random (MCAR), missing at random (MAR), or not missing at random (NMAR).

Sensitivity analyses using multiple imputation will be performed to assess the possible impact of missing data on the study results for the primary and secondary analyses. Imputation models will include the baseline covariates listed in the table above as well as intermediate outcomes as appropriate (e.g., for 24-week outcomes, the 12-week outcomes can be used in imputation models).

4 Data Monitoring

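### The primary GEE adjusts for neither site, the stratification factor, nor the baseline opioid UDT, so a small, low-cost precision gain may go unused

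*Combined protocol and SAP*

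**What the plan says.** - **Primary model (Section 3.2).** The plan states that "we will compare percentage of negative UDTs between the two groups using Generalized Estimating Equations (GEE". No covariate is named. Section 3.5 lists covariate adjustment as a modification of the primary analysis, which confirms that the primary model is unadjusted.
- **Stratification (Section 1.2).** "Randomization will be stratified by site (HMC v. BMC"). Each site has a list of 99 assignments, of which about 40 are expected to be used. No block size is stated.
- **Baseline measurement (Section 1).** "A point of care urine drug test (UDT) will also be administered at baseline and all weekly visits", and it covers opioids.
- **Where site appears.** It is in the adjusted sensitivity GEE of Section 3.5 ("We will use Generalized Estimating Equations to compare percentage of negative UDTs with adjustment for the following covariates"), in the imputation models ("All covariates listed below will be used in the imputation model provided they have less than 20% missing") and in a treatment-by-site interaction in Section 3.7 ("The primary analysis will be repeated with interaction terms between treatment arm and each of the following sub-group variables").
- **Where the baseline UDT appears.** Nowhere. The covariate table in Section 3.5 has eight rows: site, age, sex, race, ethnicity, education, prior buprenorphine treatment and homelessness. Section 3.8 says "Imputation models will include the baseline covariates listed in the table above as well as intermediate outcomes as appropriate", which leaves the list open but does not name the baseline UDT.

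**The concern.** With 80 patients, and 69% power claimed for a 20-point difference, this pilot has little precision to spare, and Section 2 says that its results will set the Phase III sample size. Two pre-treatment variables that could reduce residual variance are already collected: the stratification factor and the baseline value of the outcome itself.

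The adjusted sensitivity GEE does not fill the gap. It spends ten parameters (education has four levels, so three terms, plus seven others) and still omits the baseline UDT. The trial would therefore also fail to show, by any named analysis, how prognostic the baseline UDT is, which would be useful for designing the next trial.

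What is at stake is the width of the confidence interval, not the validity of the test.

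**Working it through.** **Inputs from the plan.** 80 patients, about 40 per arm; 50% negative under treatment as usual; a 20-point difference; 69% power; 70% completion (Sections 1.2 and 2). Level 0.05 with 95% intervals (Section 3.1), taken as two-sided. Twelve weekly tests, with missing tests coded positive apart from certain phone visits (Section 3.2). Not given: the SD or within-patient correlation, r, the share negative at baseline, and the site difference.

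**Step 1: the plan's 69%.** It can be neither reproduced nor refuted, because no SD or correlation is given. A single-test comparison of 50% with 70% at 40 per arm gives 45%, so repeated measures must have been used. Working back:

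- z(0.975) + z(0.69) = 1.96 + 0.496 = 2.456
- Implied SE = 0.20 / 2.456 = 0.0814, so the 95% half-width is 1.96 × 0.0814 = 16.0 points
- Implied patient-level SD = 0.0814 / √(2/40) = 0.364

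This SD gives 83% power for 15 points with 200 patients, in line with the plan's other sample-size statement. The implied within-patient correlation is about 0.54, so a useful r is plausible. Two things could lower r: entry may be up to 4 weeks into treatment (Section 1.1.2), and missing tests count as positive.

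**Step 2: power with site and baseline UDT added.** Power = Φ(2.456 / √[(1 − r²)k] − 1.96), where k = 1 + q/(80 − 2 − q − 1) charges for q added terms. For q = 2, k = 1 + 2/75 = 1.027. Equivalent unadjusted N = 80 / [(1 − r²)k].

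| r (assumed) | Power | Equivalent N |
|---|---|---|
| 0 | 67.9% | 78 |
| 0.2 | 69.6% | 81 |
| 0.3 | 71.9% | 86 |
| 0.35 | 73.5% | 89 |
| 0.5 | 79.9% | 104 |

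Break-even: r = √(1 − 1/1.027) = 0.16.

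**Step 3: site alone.** Here q = 1 and k = 1 + 1/76 = 1.013. The share of variance explained is (gap/2)² / 0.364². For assumed site gaps of 0, 10 and 15 points, power changes by -0.6, +0.3 and +1.3 points.

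**Step 4: the ten-parameter sensitivity model.** For q = 10, k = 1 + 10/67 = 1.149. If none of the ten terms is prognostic, power is Φ(2.456/√1.149 − 1.96) = 63.0%. It breaks even when the terms explain 1 − 1/1.149 = 13% of the variance.

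**Step 5: simulation.** 8,000 trials per setting; 80 patients; 12 tests; 50% v 70% negative after coding; 30% dropout coded positive, either unrelated or related to use; no true site gap; identity link with working independence and a small-sample-corrected robust SE. The share negative at baseline was set to 10%, 20%, 50% and 80%. Latent correlation means that between a patient's underlying tendencies at baseline and during follow-up.

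| Latent correlation (assumed) | Change in power, arm + site + baseline v arm alone |
|---|---|
| 0 | -0.7 to -1.2 points (-1.3 to -1.8 with a missing-baseline category, 5% missing assumed) |
| 0.4 | -0.3 to +0.5 points |
| 0.7 | +0.4 to +4.1 points |
| 1.0 (ceiling), 50% or 80% negative at baseline | +8.5 to +11.5 points |
| 1.0, 20% negative | +3.3 to +5.5 points |
| 1.0, 10% negative | +2.0 to +2.9 points |

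Across latent correlations 0.4 to 0.7 the interval ran from 5% narrower to 0.5% wider, a half-width of about 15.2 to 16.0 points. Type I error over 10,000 trials in each of six settings was 4.6% to 5.2% for every model, adjusted or not.

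**The case against.** An unadjusted primary analysis with a pre-specified adjusted repeat is a standard, transparent choice, and nothing in the documents contradicts it. The gain is not established: r is unknown, the large figures need perfect latent correlation, and at latent correlation 0.4 the change is close to nil. At best, short of the ceiling, the half-width falls by less than one percentage point. Site contributes almost nothing. The SAP is dated April 2021 and some research staff are unblinded, so a late change of primary model may raise doubts about pre-specification. The test kit changed in November 2019, so baseline and follow-up results may come from different kits. The simulation works on patient means, which match an independence GEE only when visit counts are equal, and some phone visits are excluded. One added row in the covariate table would show whether the baseline UDT is prognostic.

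Much of this stands as a limit on size. The gain is uncertain and probably modest, the 63% for the ten-parameter model is a worst case, and the simulated figures are approximate because of unequal visit counts and the assumed link. None of it shows that adjustment would do harm. The worst loss is 1 to 2 points of power. Different kits would mainly weaken r, and using only the four assays of the outcome removes the known difference in panel. The timing concern is real, and it is met by fixing and documenting the change before arms are compared. Absent block-size information, arm balance within site is not assured, which is a further small reason to include site.

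**Conclusion.** The concern holds as a suggestion to consider, with medium confidence about its size. The primary model omits the stratification factor and the baseline value of the outcome, and no model names the latter. The planned test remains valid. On the stated 69%, adding both terms would cost about 1 point of power if they predict nothing, change it by about -0.3 to +4.1 points under partial latent correlation (0.4 to 0.7), and add up to 11.5 points at a ceiling that is unlikely to be reached. Nearly all of any gain would come from the baseline UDT, not from site. These figures rest on assumed values for r, baseline prevalence, site gap and missing baselines, and on an SD worked back from the plan's own power.

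**What to change.** Before arms are compared, amend Section 3.2 so that the primary GEE regresses the weekly opioid-negative indicator on arm, site and baseline opioid UDT, with robust variance. In detail:

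- State the link, and report the arm effect as a marginal difference in percentage negative, so that adjustment does not change the quantity estimated.
- Define the baseline on the same four assays as the outcome: morphine, methadone, oxycodone and fentanyl.
- Confirm that the baseline sample precedes randomisation. If it does not, adjust for site only.
- Give a wholly missing baseline sample its own category, so that all randomised patients stay in the analysis.
- Add the baseline opioid UDT to the covariate table in Section 3.5, so that it also enters the adjusted and imputation models.
- Keep the unadjusted GEE as a supportive analysis.

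If the primary model cannot be changed at this stage, adding the row to the covariate table would still close the clearest gap.

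The cost is minor SAP text and analysis work, with no new data and no change to the target of 80. About 1 point of power (up to 1.8 with the missing-baseline category) is lost if neither term is prognostic. Because this alters the primary model in a SAP dated April 2021, the change and its date need to be documented.

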3.3 Secondary Analysis (Retention - Week 12)

The secondary analysis is performed to test the following hypothesis:

Secondary Hypothesis: Patients in video-DOT arm will be more likely to be engaged in office-based treatment with buprenorphine at the conclusion of the 12-week intervention period.

To evaluate the secondary hypothesis, we will use Poisson regression with robust standard errors to compare treatment groups on the proportion of participants engaged in treatment at 12 weeks (i.e. still receiving medication). The results of this analysis will be expressed as a percentage difference for video DOT compared with TAU.

Secondary Outcome Variables

1. Week 12 Post-Enrollment EHR Review (Medication information)
2. Final visit – Participant self-reports continuing treatment by confirming that they have not stopped receiving buprenorphine prescription from healthcare provider.

Additional analyses will be conducted to compare Self-Report and EHR data for patients who have both data points to assess validity.

3.4 Exploratory Hypotheses

1. Retention – 24 weeks post-randomization

- **Hypothesis:** Patients in video-DOT arm will be more likely to be engaged in office-based treatment with buprenorphine at 24 weeks post-randomization
 - To evaluate, we will use **Poisson regression with robust standard errors** to compare treatment groups on proportion of participants engaged in treatment at 24 weeks (i.e. still receiving medication) the results of this analysis will be expressed as a percentage difference for video-DOT compared with TAU. Results will be reported as a difference between proportions of patients engaged in treatment.
- **Outcome Variable**
 - Week 24 Post-Enrollment EHR Review (Medication information and discharge information)

2. Consecutive Weeks Opioid Negative Urine Tests – 12-week intervention period

- **Hypothesis:** Patients in video-DOT arm will have a higher number of consecutive weeks with research UDTs negative for opioids (non-buprenorphine) from baseline to 12 weeks post-randomization than TAU arm.
 - To evaluate, we will use **t-test with unequal variance** to compare the mean number of consecutive weeks with negative UDTs between treatment arms. Results will be reported as an estimate of the difference in means.

- **Outcome Variable:**
 - 12 Research-UDTs for 5 Opioid Assays (F/U Visits 1-11, and Final) negative for all of the following:
 - Morphine, Methadone, Oxycodone, Fentanyl

3. Opioid Use Self-report – Final visit

- **Hypothesis:** At final visit, patients in video-DOT arm will self-report fewer days using illicit opioids in the past 30 days than TAU arm.
 - To evaluate, we will use a **Poisson regression with robust standard errors** to compare treatment groups on proportion of participants who self-report use in past 30 days at week 12. Results will be reported as a difference between proportions of participants who report illicit opioid use at week 12.
- **Outcome Variable:**
 - Final Visit – ASI Past 30 days w/o prescription or in greater amounts than prescribed (i.e. illicit use)
 - Heroin, Buprenorphine, Methadone, Fentanyl, Other prescription opioids

4. Buprenorphine Adherence Self-Report – 12-week intervention period

- **Hypothesis:** Patients in video-DOT arm will self-report higher percentage of days adherent to their prescribed buprenorphine between Baseline and 12 weeks post-randomization than TAU arm.
 - To evaluate, we will use **Poisson regression with robust standard errors** to compare treatment groups on participants' proportion of self-reported days adherent to buprenorphine over the 12-week intervention period. Results will be reported as a comparison between groups on the percentage of days adherent.
- **Outcome Variables:**
 - F/u 1 -11 Visit – Adherence Follow-up Timeline Follow-back
 - Final – Treat Final (i.e. Adherence final) Timeline Follow-back

5. Time to occurrence of non-retention (discharge) – 24 weeks post-randomization

- **Hypothesis:** Patients in video-DOT arm will have longer time to discharge than TAU arm from baseline to 24 weeks post-randomization
 - To evaluate, we will use **Kaplan-Meier survival curves** and a log-rank test. Results will be reported using a hazard ratio.
- **Outcome Variable:**
 - 24 Week Post-Enrollment EHR Review – Discharged (Y/N) and Date of Discharge

6. Buprenorphine Non-Use – 12-week intervention period

- **Hypothesis:** Patients in video-DOT arm will have a lower percentage of at least one weekly study UDT negative for buprenorphine than TAU arm over the 12-week intervention period.

- To evaluate, we will use **Poisson regression with robust standard errors**. Results will be reported as a difference in percentage of having at least one UDT negative for buprenorphine.
- **Outcome Variable:**
 - F/U 1-11, Final Visits – 12 Research UDT Buprenorphine assay results

7. Stimulant Use – Final visit

- **Hypothesis:** At final visit, patients in video-DOT arm will have a lower percentage of UDTs positive for stimulant substances than the TAU arm.
 - To evaluate, we will use **Poisson regression with robust standard errors** to compare the percent of patients' UDTs positive for stimulants.
- **Outcome Variables:**
 - Final Visit – Research UDT Stimulant Panels
 - Positive for stimulants = positive for Cocaine, Amphetamines, or methamphetamines. If “missing” count as positive.

8. Treatment Satisfaction – Final visit

- **Hypothesis:** At final visit, patients in the video-DOT arm will report higher satisfaction with clinic's treatment of OUD than TAU arm.
 - To evaluate, we will use **t-test with unequal variance**. Results will be reported as a difference between mean satisfaction scores (1-5).
- **Outcome Variable:**
 - Final Visit – Likert Scale – Participant's satisfaction with clinic helping participant manage their OUD
 - Likert Scale Options
 1. Very Dissatisfied
 2. Dissatisfied
 3. Neutral
 4. Satisfied
 5. Very Satisfied

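### Exploratory outcome 6 (any buprenorphine-negative study UDT) makes no allowance for the number of tests taken, so unequal research-visit attendance between arms would distort the comparison

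*Combined protocol and SAP*

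**What the plan says.** Section 1.3 lists exploratory outcome 6 as a yes/no result per participant: at least one buprenorphine-negative study UDT at any time in the 12 weeks. Section 3.4, item 6, states the hypothesis as "Patients in video-DOT arm will have a lower percentage of at least one weekly study UDT negative for buprenorphine than TAU arm". The data are the 12 study tests (follow-up visits 1 to 11 and the final visit). The analysis is Poisson regression with robust standard errors, reported as a difference in percentages. Item 6 gives no denominator, offset, minimum number of tests or rule for missed tests. The next item, on stimulants, does give a rule: "If “missing” count as positive".

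Four other places bear on missing tests:

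- Section 3.8 gives a general rule, "we will assume that missing UDT results are positive (unless a visit was conducted by phone due to COVID-19", without naming an assay.
- Section 3.5 describes that assumption in terms of opioids when it introduces multiple imputation: "rather than assuming all missing are opioid positive". Section 3.2 attaches it to the primary analysis.
- Section 3.8 also promises: "Patterns of missing urine samples will be described and compared between treatment arms". It describes multiple imputation as intended "to assess the possible impact of missing data on the study results for the primary and secondary analyses", but then gives an exploratory example: "for 24-week outcomes, the 12-week outcomes can be used in imputation models".
- Section 3.2 covers COVID-19 phone visits, at which no study UDT was collected. "If a clinical UDT result is also not available for a particular phone visit", that visit is left out of the primary analysis.

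**The concern.** An any-negative outcome depends on two things: how often a test is negative, and how many tests there were. Item 6 does not separate them. A participant who leaves after three visits has three chances to be counted, and one who attends throughout has twelve.

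Test counts are likely to vary between participants. Section 2 expects 70% to complete the intervention period, and phone visits yielded no study sample. This harms the arm comparison only if the counts differ by arm. The secondary hypothesis (section 3.3) is that video-DOT keeps more people in treatment. Treatment engagement is not the same as research-visit attendance, but if the two move together, item 6 would count better retention against video-DOT. If video-DOT lost more people from research visits, the error would run in its favour.

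Item 6 is the plan's only urine-based comparison of buprenorphine use between arms (item 4 is self-report), and section 2 says the pilot's results will inform the size of a Phase III trial.

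A secondary point is that the general rule in 3.8 changes direction on this assay. For opioids and stimulants, positive is the unfavourable result. For buprenorphine, it means medication present.

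**Working it through.** The documents give no expected rate for item 6, so there is no figure to reproduce. What follows is an illustration.

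**Inputs from the documents:** up to 12 tests (3.4, item 6); target sample size 80 (1.2), taken as about 40 per arm; 70% expected completion (section 2).

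**Assumptions not in the documents:** weekly risk q of a buprenorphine-negative test of 5% or 10%; independent tests; completers take all 12 tests; non-completers take k = 0 to 11 tests with equal probability; completion c differs by arm.

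**Formulas.** P(any negative in n tests) = 1 − (1 − q)^n. Arm value = c × P(12) + (1 − c) × mean of P(k) over k = 0 to 11.

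**Step 1: no true effect, completion 80% vs 60%.**

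- q = 5%: P(12) = 46.0% and the non-completer mean is 23.4%. The arms show 0.8 × 46.0 + 0.2 × 23.4 = 41.4% and 0.6 × 46.0 + 0.4 × 23.4 = 36.9%, a gap of 4.5 points against the better-attending arm.
- q = 10%: P(12) = 71.8% and the mean is 40.2%. The arms show 65.4% and 59.1%, a gap of 6.3 points.

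**Step 2: how the gap varies (points, q = 5% / 10%).**

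| Scenario | Gap |
|---|---|
| 80% vs 60% | 4.5 / 6.3 |
| 80% vs 60%, no-test participants excluded | 3.9 / 5.4 |
| 80% vs 60%, within-person correlation 0.2 (beta-binomial) | 2.1 / 3.4 |
| 75% vs 65% | 2.3 / 3.2 |
| 75% vs 65%, correlation 0.2 | 1.0 / 1.7 |
| Equal completion | 0 |

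**Step 3: leavers at higher risk than stayers (stayers 5%, completion 80% vs 60%).** The benchmark is what complete testing would show. Distortion = observed difference − complete-testing difference, each taken as better-attending arm minus the other.

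| Leaver risk | Observed difference | Complete testing | Distortion |
|---|---|---|---|
| 5% | +4.5 | 0.0 | 4.5 |
| 8% | +2.4 | −3.5 | 5.8 |
| 10% | +1.2 | −5.2 | 6.3 |
| 12% | +0.1 | −6.5 | 6.6 |
| 20% | −3.0 | −9.4 | 6.4 |

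(Rows are computed before rounding.) The observed difference shrinks and then changes sign, but the distortion remains.

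**Step 4: a true 20% relative reduction in the better-attending arm (5% to 4%, or 10% to 8%).** Complete testing would show −7.2 or −8.5 points. Item 6 shows −6.3 or −7.8 at equal 70% completion, −4.2 or −4.8 at 75% vs 65%, and −2.1 or −1.7 at 80% vs 60%.

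**Step 5: precision.** With 40 per arm, SE = √(0.414 × 0.586/40 + 0.369 × 0.631/40) = 10.9 points.

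**Step 6: what the 3.8 rule would change.** Coding a missed test as buprenorphine-positive never creates a negative. It gives the same result as using observed tests only, except for people with no test, who become non-events instead of dropping out. In this model they are (1 − c)/12 of the arm: 0.3/12 = 2.5%, or about 1 in 40, at 70% completion. Excluding them moves the gap only from 4.5 to 3.9, or from 6.3 to 5.4.

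**The case against.** The strongest reply is that the problem is hypothetical and small. All participants follow the same visit schedule (section 1), no passage predicts different attendance by arm, and the weekly risk, dropout pattern and completion gap above are assumptions. Completing the intervention period is not a count of tests. Item 6 is one of eight exploratory outcomes in a pilot of 80, and every no-effect gap shown is well below the standard error. Section 3.8 already compares missing-urine patterns by arm. All of this stands, and it limits the severity. It does not remove the point: the planned comparison of patterns would reveal an imbalance but would not correct item 6, and the imputation is not clearly extended to it.

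Three stronger readings are tempting, and the documents do not support them:

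- *The plan codes missed buprenorphine tests as medication present.* The 3.8 sentence names no assay, but 3.2 and 3.5 tie the rule to opioids, and item 7 states its own rule separately. Even if the rule did apply, it would affect only people with no test.
- *Item 6 will be biased against video-DOT.* The direction depends on which arm attends better, which the documents do not say.
- *The comparison risks a false significant result.* With a standard error of about 11 points, the concern is a distorted estimate.

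A reader might also infer that the problem disappears if leavers are at higher risk, because the observed gap then closes. Step 3 shows otherwise: complete testing would itself have shown a difference, and item 6 hides it.

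**Conclusion.** The point holds as a minor one. Item 6 mixes medication use with the number of tests taken, and nothing in the plan corrects for this. If research-visit attendance differs by arm, the comparison is biased against the better-attending arm. With equal attendance and no true effect there is no bias.

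Under the stated assumptions the distortion is 4.5 or 6.3 points at 80% vs 60% completion with no effect, and 1.0 to 3.4 points with a smaller completion gap, within-person correlation, or both. It is 4.5 to 6.6 points for leaver risk between 5% and 20% with stayers at 5%. A true benefit in the better-attending arm could be largely masked. The omission is certain; the size is only illustrative. The unstated reach of the 3.8 rule is a matter of wording with little numerical effect. The primary and secondary analyses are not affected.

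**What to change.** 1. **In 3.4, item 6,** keep the any-negative outcome and add that it uses observed study UDTs only; that the missing-as-positive rule in 3.8 does not apply to the buprenorphine assay; and that participants with no buprenorphine result are excluded from item 6 and counted by arm. Report the number of buprenorphine tests per participant by arm.
2. **Add a companion analysis.** Apply the GEE already planned for the primary outcome to the weekly study buprenorphine result on tests taken, and repeat it with multiple imputation. Use the same imputed weekly results to re-derive the any-negative outcome.
3. **Use one data source, study UDTs, for both.** Any use of clinical results at phone visits should be a labelled sensitivity analysis applied to both.

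The cost is a few lines of text and a little more analysis. Section 1.3 is unchanged, and the weekly study results and the model are already in the plan. Clinical buprenorphine results would need extracting only for the optional sensitivity analysis.

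The companion has limits. It answers a per-test question, and on tests taken it assumes that missed tests are missing completely at random (at random with imputation). If leavers' risk were 12% against 5% for stayers, at 80% vs 60% completion, the pooled per-test share (12c × 0.05 + 5.5(1 − c) × 0.12) / (12c + 5.5(1 − c)) would be 5.7% vs 6.6%, where complete testing would show 6.4% vs 7.8%. That keeps the direction but understates the difference. The any-negative outcome in the same case shows 45.9% vs 45.8%, where complete testing would show 52.5% vs 59.0%.
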